The patients will be assessed at baseline, 2 weeks post intervention, after completion of GLA:D and 6, 12- and 24- months post cryoneurolysis. The tests will include both patient-reported outcomes (PRO) and objective functional performance tests. The effects of group CRYO and group SHAM will be compared at each timepoint (Table 1).

Primary outcome

The primary outcome is the change in patient reported knee pain intensity assessed using the numeric rating scale (NRS) from baseline to 2 weeks post cryoneurolysis compared between group CRYO and SHAM. NRS consists of an 11-point scale between 0 and 10-, anchored by two verbal descriptors, "no pain" for the score of 0 and "worst pain imaginable" for the score of 10. Respondents are asked to rate their pain intensity on average within the past 24 h. The NRS instrument has been validated in diverse populations and has been widely applied in clinical and research settings [37].

Secondary outcomes

Functional performance will be evaluated by the 30 s chair-stand test, the 40 m fast-paced walk test, the 9-step stair-climb test and isometric knee MVC force [38].

The 30s chair-stand test [39] consists of repeated sitto-stand movement for a duration of 30 s. The starting position is seated, with feet placed flat on the floor, shoulder width apart and with the arms crossed on the chest. The position change to standing, with hips and knees fully extended, followed by sitting back down, with bottom fully touching the seat. The test is performed with usual footwear and the chair should be with a straight back, with no arms, placed against a wall. In cases where the movement cannot be performed even once, the hands are allowed to be placed on the legs or a regular mobility aid can be used - the result is then reported as an adapted test score. The outcome is the total number of complete chair stands performed for the duration of the task (one chair stand represents a stand followed by a sit movement).

[figure not shown]
The 40 m fast paced walk test [40] consists of walking as fast as possible, but still safely, along a 10 m marked walkway, then turning around a cone / tape and return. This is then repeated for a total distance of 40 m. The test is performed with usual footwear and regular walking aid is allowed and recorded. The outcome is expressed as speed. i.e. walking distance (40 m) divided by the time to perform the task (s). Timing is paused during turns.

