The planned number of trial participants is based on the null-hypothesis, assuming no difference between cryoneurolysis treatment and sham. Estimating the sample size for a two-sample means test with a level of significance at 0.05, assuming a common standard deviation (SD) of 3 in NRS pain intensity scores indicates that for the intention-to-treat (ITT) population, 74 individuals is required to obtain a power of at least 80% to establish a minimal clinically important difference (MCID) of 2 in NRS pain scores [47]. The MCID and common standard deviation is based on previous findings with a similar patient group and intervention [48]. With an expected drop-out rate of 20%, a total of 94 individuals will be included in the project, 47 in each group.

Statistical methods

To evaluate the distributions of the continuous outcomes, visual inspection of the studentized residuals will be applied to evaluate whether the assumption of normality is reasonable. Data will be reported as differences between group means (means ± standard deviations, 95% CIs) if normal distributed, otherwise as medians with interquartile ranges. Categorical data will be reported as numbers and proportions. An Intention-To-Treat (ITT) analysis will be used for all allocated patients. Mixed linear regression with the assumption of unstructured covariance will be used to model the effect of the cryoneurolysis treatment over time and to take into account the repeated measures by including individuals as random variables. Time, group of treatment (cryoneurolysis or SHAM) and the Group, time interaction will be used as fixed effects to estimate different patterns of change over time. The results will be illustrated using marginal effects that will be calculated using the margins command of STATA16. If the 95% CIs do not overlap, data will be considered statistically significant. A statistically significant difference of at least two in NRS scores between groups, will be interpreted as a MCID.

Table 1 Timeline of the study – outcomes and variables assessed during the trial period

Timepoint	Study period									
	Enrolment		Allocation	Post-allocation			Follow-up			
	-4w	-1w	0w	2w	10w	na	24w	48w	96w	
Enrolment:										
Eligibility screening	Х									
Informed consent	Х									
Genicular nerve block		Х								
Allocation			Х							
Interventions:										
Cryoeurolysis (CRYO)			Х							
Sham treatment (SHAM)			Х							
GLA:D (SHAM & CRYO)				Х	Х					
Assessments:										

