The inclusion of a sham group is necessary to test the hypothesis because of the large reported placebo effects in invasive interventions [49]. In addition, the associated risks are minimal and the nature of misleading, in regards to the administration of the sham trial, will be adequately disclosed and accepted by the patient during the informed consent process. The sham group is implemented according to current standards [50].

Discussion

Impact and significance of the study

Current pain-relieving therapies show small to moderate effects and a significant portion of patients who receive surgery (TKA) report unchanged pain intensity levels post-surgery. This indicates that there is a need for additional therapies that could supplement or improve the existing therapies. A significant difference in the change in pain intensity between sham and intervention post cryoneurolysis treatment would indicate that cryoneurolysis is an effective non-pharmacological therapeutic option to treat pain in OA patients. Outcome measures include both pain, social and psychological factors and functional capacity, which allows for a thorough understanding of treatment effects. The novel addition of GLA:D in combination with cryoneurolysis will elucidate whether feasibility and effectiveness of exercise increase if pain is attenuated and if the potential pain-relieving effects of cryoneurolysis can be extended. The potential benefits include increased functional capacity and quality of life as a result of significant pain relief and improved benefits of physical exercise, ultimately postponing or making surgical intervention unnecessary. This could have a significant impact on patients' lives as well as significant socioeconomic consequences and could change the clinical landscape in the treatment of OA. Finally, an important perspective, is the application of cryoneurolysis in other areas - such as managing pain, related to surgery, to improve rehabilitation.

If the results indicate that cryoneurolysis does not elicit additional pain relief when compared to sham, it might indicate that cryoneurolysis treatment is not suitable for the treatment of OA related pain or at least not in the way it is applied in the current study.

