The Efficacy of Cryoneurolysis on Chronic Pain in Patients with Knee Osteoarthritis; A Double-blinded Randomized Controlled Sham Trial

Date: 30-09-2024 Clinicaltrials.gov; NCT03774121

Analysis plan

To assess the distribution of continuous outcomes, a visual inspection of the studentized residuals was performed to determine if the assumption of normality was appropriate. Both an Intention-To-Treat (ITT) analysis and a per-protocol (PP) analysis were conducted for all assigned patients. Mixed linear regression with the assumption of unstructured covariance was employed to model the effect of cryoneurolysis treatment over time, accounting for repeated measures by treating individuals as random variables. Fixed effects included time, treatment group, baseline pain levels, and the interaction between group and time, to estimate changes over time. The results are presented as predicted average values and predicted differences between groups, representing the estimated outcomes for each group while considering random effects and covariates included in the model. These are illustrated using marginal effects calculated with the margins command in Stata16. A P-value of less than 0.05 was considered statistically significant. For the primary outcome—average pain over 24 hours on the numeric rating scale—the p-value was adjusted for multiple comparisons (k=9) using the Holm-Bonferroni correction for the mixed effects model. Secondary outcomes were not adjusted, as these were exploratory in nature.

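### Read as the two group intervals, the protocol's CI-overlap rule tests at about 0.0056, not the 0.05 behind its sample size, and no text says the SAP's p-value rule replaces it

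*Protocol*

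**What the plan says.** The Sample size section of the protocol plans the trial as follows: "Estimating the sample size for a two-sample means test with a level of significance at 0.05", with a common SD of 3, a difference of 2 NRS points and power of at least 80%. This gives 74 evaluable patients, raised to 94 (47 per arm) for 20% dropout.

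The Statistical methods section fits a mixed model with time, group and their interaction. It then says: "The results will be illustrated using marginal effects that will be calculated using the margins command of STATA16". The next sentence is the decision rule: "If the 95% CIs do not overlap, data will be considered statistically significant". A further sentence builds on it: "A statistically significant difference of at least two in NRS scores between groups, will be interpreted as a MCID". Earlier, the same section promises between-group mean differences with 95% CIs. The Outcomes section says: "The effects of group CRYO and group SHAM will be compared at each timepoint".

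The SAP has no overlap rule. It says: "The results are presented as predicted average values and predicted differences between groups". It calls p below 0.05 significant, applies Holm-Bonferroni with k=9 to the primary outcome, and leaves the secondary outcomes unadjusted as exploratory. It does not mention the protocol's rule.

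**The concern.** Comparing two separate 95% CIs for overlap is not a 5% test of the difference. The rule adds the two half-widths, whereas the standard error of a difference combines the two errors in quadrature. The result is a much stricter test than the one the trial was sized for.

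Two things are at stake.

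- **Power for the primary comparison.** If the overlap rule is applied, the stated power of at least 80% does not hold, and a real 2-point effect is missed far more often than planned. The Discussion says that if results show no added relief over sham, "it might indicate that cryoneurolysis treatment is not suitable for the treatment of OA related pain", with the qualification that the fault may lie in how it was applied here. A miss caused by the decision rule could be read that way.
- **Two answers from one dataset.** For secondary outcomes, the same result can be significant under the SAP and not significant under the protocol.

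**Working it through.** **Inputs (protocol, Sample size and Randomization).** Alpha 0.05, SD 3 in both arms, difference 2, power at least 80%, 74 evaluable (37 per arm), 94 enrolled (47 per arm), 1:1 allocation. Sidedness is not stated. Two-sided reproduces 74; one-sided would give about 56.

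**1. The plan's own figure.** Normal formula: n per arm = 2 × (1.960 + 0.842)² × 3² / 2² = 35.3, so 36. The t-test gives 79.7% power at 36 and 80.8% at 37, so 37 per arm, 74 in total. Dropout: 74 / 0.8 = 92.5, so 93, or 94 for equal arms. The stated figures are reproduced.

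**2. Alpha of the overlap rule.** Two 95% CIs fail to overlap when |difference| > 1.96 × (SE₁ + SE₂). The SE of the difference is √(SE₁² + SE₂²). With k = SE₂/SE₁, the critical value is 1.96 × (1 + k) / √(1 + k²).

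| SE ratio k | Critical value | Two-sided alpha |
|---|---|---|
| 1 | 2.772 | 0.0056 |
| 1.25 | 2.755 | 0.0059 |
| 1.5 | 2.718 | 0.0066 |
| 2 | 2.630 | 0.0085 |

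With 1:1 allocation and a common SD, k is close to 1.

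**3. Difference needed at 37 per arm.** The SE of the difference is 3 × √(2/37) = 0.6975.

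- Overlap rule: 2 × 1.96 × 3/√37 = 1.93 points (2.00 with t-based intervals, 36 df).
- Test at 0.05: 1.96 × 0.6975 = 1.37 points (1.39 with t, 72 df).

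**4. Power at a true difference of 2, SD 3, no baseline adjustment.** Power is Φ(2/SE − critical value). At 37 per arm, 2/0.6975 = 2.867, giving Φ(2.867 − 2.772) = 0.538 and Φ(2.867 − 1.960) = 0.818.

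| Evaluable per arm | Overlap rule, normal / t | 0.05 test, normal / t |
|---|---|---|
| 37 | 53.8% / 50.8% | 81.8% / 80.8% |
| 47 | 67.7% / 65.3% | 89.8% / 89.2% |

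A simulation of 100,000 trials with group-specific SEs at 37 per arm agrees. Non-overlap occurs in 50.8% (t-based CIs) or 54.5% (normal CIs) of trials at a difference of 2, and in 0.55% or 0.74% under the null.

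**5. Size needed for 80% power under the overlap rule.** 59 (normal) or 61 (t) per arm, so 118-122 evaluable patients against 74.

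**6. Secondary outcomes.** The two documents disagree when the observed difference lies between 1.96 × √(2/n) and 2.772 × √(2/n) SDs.

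- n = 37: 0.46 to 0.64 SD (t: 0.46 to 0.67).
- n = 47: 0.40 to 0.57 SD (t: 0.41 to 0.59).

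The documents give no effect sizes for these outcomes. For assumed true effects of 0.3, 0.5 and 0.8 SD at 37 per arm, 18%, 31% and 18% of comparisons fall in that zone (t: 18%, 32%, 21%).

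**7. The SAP's primary-outcome threshold.** Holm's strictest step is 0.05/9 = 0.00556, almost the same as the overlap alpha. Power there at 37 per arm is 53.8% (normal) or 50.7% (t).

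**8. MCID label (significant and observed difference of at least 2).** Simulation at 37 per arm gives 46.6% under overlap with t-based CIs and 49.9% under p<0.05.

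**The case against.** **The SAP probably governs.** The protocol's appendix gives version 1, 21 January 2021. The SAP is in the past tense, adds baseline pain to the model, adds a per-protocol analysis and adds Holm, so it reads as a later replacement of the statistics section. That is likely, but it is inference: both cover pages carry 30-09-2024, and no sentence states which rule prevails. A past-tense plan also leaves open when the rule changed relative to unblinding.

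**Another reading is possible.** The authors may have meant that the CI of the difference excludes zero. That would be an ordinary 0.05 test and the problem would disappear. But overlap needs two intervals, the preceding sentence concerns model margins, and groups are compared at each timepoint. Even if the other reading was meant, the sentence needs rewording.

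**For the primary outcome the SAP may be just as strict.** This stands. At Holm's first step the two rules nearly coincide, and only later steps are looser. The clear conflict between the documents is therefore in the secondary outcomes. It does not restore the stated 80%.

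**37 per arm without baseline adjustment is the low end.** This also stands. The endpoint is at 2 weeks, and the protocol does not say when the 20% dropout falls. Adjusting for baseline, which only the SAP does, with an assumed correlation of 0.3-0.5 (not in the documents), would put overlap-rule power at 56-71% with 37 per arm and 71-83% with 47.

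**The damage is limited.** The rule is conservative, the secondary outcomes are called exploratory, and the MCID label hardly moves. These points limit the severity; they do not remove the mismatch.

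**Conclusion.** The concern holds and should be fixed, though it does not threaten the type I error. On the natural reading, the protocol's rule has an alpha of about 0.0056 and does not match the sample size in the section just before it. A true 2-point effect would be missed in about 46-49% of trials at 37 per arm, instead of 18-19%. This rests on independent group estimates with similar SEs, SD 3 and no baseline adjustment. The alpha is robust to moderately unequal SEs; the power depends on how many patients are evaluable at 2 weeks. The two documents give different significance calls on secondary outcomes in the range set out above, and neither says which rule prevails.

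**What to change.** - Delete the overlap sentence from the protocol. Since that text is a published article, a dated note withdrawing it may have to serve.
- Judge significance from the model-based between-group contrast at each timepoint, with its own 95% CI and p-value, as the SAP already does.
- State in that note that the SAP rule replaces the overlap rule, and whether this was decided before unblinded results were seen.
- Give the power that matches the alpha applied to the 2-week comparison: about 81% with 74 evaluable at 0.05, or about 51-54% if it must pass Holm's strictest step, both before baseline adjustment. If analysis has already been done, label this as retrospective.

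Which comparisons make up the nine in the Holm family is a separate question.

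The cost is small. The contrast comes from the model already fitted and needs no new data; the rest is one withdrawn sentence, one note and one power statement.

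### The 80% power quoted for an MCID of 2 is the power to reject no difference; if the true difference is 2, the protocol's MCID rule is met only about half the time

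*Protocol*

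**What the plan says.** The Protocol's Sample size section starts from a null hypothesis of zero: "The planned number of trial participants is based on the null-hypothesis, assuming no difference between cryoneurolysis treatment and sham". It names a two-sample means test at the 0.05 level with a common SD of 3, and says that 74 individuals are needed "to obtain a power of at least 80% to establish a minimal clinically important difference (MCID) of 2 in NRS pain scores". Allowing for 20% drop-out gives 94, or 47 per arm.

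The Statistical methods section then sets the interpretation rule: "A statistically significant difference of at least two in NRS scores between groups, will be interpreted as a MCID". The sentence just before it defines significance: "If the 95% CIs do not overlap, data will be considered statistically significant". Neither document gives another rule for calling a result an MCID, and neither gives a power for this one.

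The SAP does not repeat or withdraw the MCID rule. It defines significance differently: "A P-value of less than 0.05 was considered statistically significant". For the primary outcome it adds that "the p-value was adjusted for multiple comparisons (k=9) using the Holm-Bonferroni correction for the mixed effects model".

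The efficacy conclusion in the Protocol's Discussion rests on significance alone: "A significant difference in the change in pain intensity between sham and intervention post cryoneurolysis treatment would indicate that cryoneurolysis is an effective" treatment option.

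**The concern.** The power sentence and the MCID rule use the same term and the same value of 2. Read together, they suggest that if cryoneurolysis truly lowers pain by 2 points more than sham, the trial has at least an 80% chance of a result labelled an MCID. The sample size calculation does not deliver that. It covers only the chance of rejecting zero. The label also requires the observed difference to reach 2, and because that threshold equals the assumed effect, the estimate falls short of it about half the time.

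What is at stake is the reading of clinical importance. If the label is missed, someone relying on the 80% could take this as good evidence that the true effect is below 2. If it is awarded on an estimate near 2, the data may still be compatible with much smaller differences.

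**Working it through.** **Inputs (Protocol, Sample size and Statistical methods; SAP).** Difference 2; SD 3; level 0.05; 37 per arm before drop-out and 47 per arm as recruited; Holm-Bonferroni with k = 9. Sidedness is not stated. Two-sided reproduces the plan's figure, while one-sided gives 56 in total and does not.

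**1. The plan's own figure.** SE = 3 × √(2/n), which is 0.6975 at 37 per arm and 0.6189 at 47. Noncentral-t power at a true difference of 2 is 79.7% at 36 per arm, 80.8% at 37 and 89.2% at 47. So 37 per arm, 74 in total, is right. For drop-out, 74 / (1 − 0.20) = 92.5, and 94 with equal arms covers it.

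**2. Observed difference needed for significance (at the planning SD).**
- t-test: t(0.975, 2n−2) × SE = 1.390 (37 per arm), 1.229 (47).
- Non-overlap of the two group-mean 95% CIs: 2 × t(0.975, n−1) × 3/√n = 2.000, 1.762.
- Strictest Holm step, 0.05/9: 1.994, 1.757.

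**3. Chance of meeting the MCID rule.** Approximately, P = 1 − Φ((max(2, c) − δ)/SE), where c is the significance threshold and δ the true difference. With δ = 2 and c below 2, this is 1 − Φ(0) = 0.50 for any SE. Where c is close to 2, sampling variation in the SD lowers it. Simulation, 1,000,000 trials per case, true difference 2, SD 3:

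| Significance criterion | Per arm | Significant | Significant and ≥ 2 (label) | Significant but < 2 |
|---|---|---|---|---|
| Unadjusted t-test | 37 | 80.8% | 50.0% | 30.8% |
| Unadjusted t-test | 47 | 89.2% | 50.0% | 39.3% |
| CI non-overlap | 37 | 50.8% | 46.7% | 4.1% |
| CI non-overlap | 47 | 65.3% | 49.9% | 15.4% |

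The t-test significance figures are the exact powers from step 1. At 0.05/9 the label is met 46.6% and 49.9% of the time, and significant-but-below-2 occurs 4.1% and 15.3% of the time.

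**4. Effect of sample size.** Under the t-test the label is still met 49.9% of the time at 94 and at 200 per arm. The chance falls below half only in trials smaller than roughly 18 per arm, so the planned sizes are well clear of that.

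**5. True difference needed for an 80% chance of the label (t-test).** 2 + 0.8416 × SE = 2.59 at 37 per arm and 2.52 at 47.

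**6. What an observed 2.0 supports.** 2.0 ± 1.390 = 0.61 to 3.39 at 37 per arm; 2.0 ± 1.229 = 0.77 to 3.23 at 47.

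**Sensitivity to the SD.** The Protocol gives the SD of 3 for NRS scores and does not give the SD of change. For SDs of 2 to 4, the t-test result in step 3 stays between 49.4% and 50.0%. The non-overlap result at 37 per arm does depend on the SD: 50.0% at SD 2.5 and 35.0% at SD 3.5. The interval in step 6 at 37 per arm runs from 1.07–2.93 (SD 2) to 0.15–3.85 (SD 4).

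**The case against.** Sizing a trial to reject zero, with the MCID as the alternative, is standard practice, and the Protocol names the null hypothesis in the same paragraph. An unbiased estimate falls below its true value half the time in any trial, so the 50% is not peculiar to this one. The objective is superiority to sham, the Discussion's efficacy statement needs only significance, and the SAP does not carry the MCID rule forward. All of this stands. It limits the point to what the power sentence claims next to the rule that follows it; it does not make the 80% apply to that rule.

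Four stronger readings are tempting, and the documents do not support them.
- *The sample size is wrong.* It is not: 74 and 94 reproduce for the stated test.
- *About a third of trials would reject zero yet miss the label.* The 31% and 39% hold only for an unadjusted t-test. Under the Protocol's non-overlap criterion or 0.05/9 they fall to 4% and 15%. At 37 per arm most of the gap from 80% then comes from the stricter significance criterion, which is a separate matter not argued here.
- *The superiority conclusion is undermined.* It does not depend on the label.
- *The MCID rule should be replaced by one based on where the CI lies.* Requiring the whole interval to be at or above 2 would be close to a margin-superiority criterion for which the trial was not sized: it would be met 2.5% of the time at a true difference of 2, and 29% (37 per arm) or 36% (47 per arm) at 3. Since the SAP is written in the past tense, such a replacement could also be post hoc.

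**Conclusion.** The point holds as a misstatement of what the quoted power covers. If the true difference is 2, the chance of rejecting zero by the t-test is 80.8% at 37 per arm and 89.2% at 47. The chance of meeting the Protocol's MCID rule is about 50% under the t-test, and 47% (37 per arm) to 50% (47 per arm) under CI non-overlap or the strictest Holm step. A larger trial does not lift it above about half.

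The 50% rests only on the estimate being centred on the true difference and on an observed 2 already being significant. The 47% also assumes an SD of 3 and t-based group-mean intervals; with z-based intervals it is 48.2%. The consequence is confined to interpretation: missing the label is not evidence that the effect is below 2, and receiving it on an estimate near 2 does not exclude smaller effects.

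**What to change.** 1. Reword the sample size sentence along these lines: at least 80% power to reject no difference (two-sided 0.05 t-test) if the true between-group difference in NRS is 2 (SD 3). Add that the chance of then meeting the MCID rule is about 50%, so missing the label does not show that the effect is below 2.
2. Keep the prespecified MCID label. Whenever it is applied or withheld, report the 95% CI of the 2-week between-group difference and say whether it includes 2. The Protocol already plans this interval for normally distributed data ("Data will be reported as differences between group means", with 95% CIs). The SAP mentions no interval, so the requirement should be written there too.
3. Record both as a dated clarification and, given the SAP's past tense, state whether results were known at that date.

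This needs no new data and no change to the number of patients. The cost is a less favourable stated chance of an MCID result, about 50% where a reader might have assumed 80%. Most results will also be described as compatible with differences on both sides of 2: at a true difference of 2, the interval includes 2 in 95% of trials.
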